## **2.6.5 Supportive analyses**

Sensitivity analyses will be performed as follows: co-primary endpoints (PASI 75 and IGA mod 2011 0 or 1 response at Week 12) and the key secondary endpoint (PASI 90 at Week 12) will be evaluated using the (exact) logistic regression as described in primary analysis method with pure non-responder imputations instead of multiple imputations for missing values.

## **2.7 Analysis of the key secondary objective**

### **2.7.1 Key secondary endpoint**

The secondary variable in testing strategy is the PASI 90 response of subjects with severe chronic plaque-type psoriasis at Week 12 (for superiority comparison of secukinumab doses versus placebo). The PASI 90 response of subjects with severe chronic plaque-type psoriasis at Week 12 will be analyzed in the same way as the primary variables.

The secondary efficacy variable PASI 90 at Week 12, will be analyzed using the FAS unless otherwise specified.

### **2.7.2 Statistical hypothesis, model, and method of analysis**

The family-wise type I error will be set to  $\alpha=2.5\%$  (one-sided). The graphical approach of Bretz ([Bretz et al 2009](#)) for sequentially rejective testing procedures is used to illustrate the hierarchical testing strategy. The procedure allows the type I error rate associated with a rejected hypothesis to be reallocated according to a set of pre-specified rules. The hypotheses associated to the primary and secondary variables are as below.

#### **Co-primary variables:**

H1 to H4 (see [Section 2.6.3](#))

[figure not shown]
#### **Secondary variable:**

H5: secukinumab low dose is not superior to placebo with respect to PASI 90 response at Week 12

H6: secukinumab high dose is not superior to placebo with respect to PASI 90 response at Week 12

The graphical approach of Bretz (Bretz et al 2009) for sequentially rejective testing procedures is used to illustrate the testing strategy in Figure 2-1.

**Figure 2-1** Testing strategy

One-sided p-values will be derived. The family-wise error will be set to  $\alpha=2.5\%$  (one-sided). The hypotheses are mapped into two sets (H1, H3 and H5) or (H2, H4 and H6) such that hypotheses within a set correspond to the same secukinumab (AIN457) dose regimen. In essence, the type-I-error probability will be equally split for both sets of hypotheses and within each set, the hypothesis will be tested sequentially as follows:

Within each pair, of hypotheses (H1 or H3) and (H2 or H4), each hypothesis is tested at  $\alpha/2$  (one-sided). Only if both hypotheses of a pair are rejected, then the testing sequence will continue.

In the next step of the sequence, the null hypotheses corresponding to the PASI 90 comparison of secukinumab (AIN457) versus placebo will be tested. H5 and H6 will be tested at  $\alpha/2$  (one-sided).

If all hypotheses within a set referring to a secukinumab dose regimen are being rejected, i.e., either (H1, H3 and H5) or (H2, H4 and H6), then the corresponding type I error probability can be passed on to the other set of hypotheses, and if needed, hypotheses can be retested at a higher significance level.

### 2.7.3 Other Efficacy variables

## PASI 75, PASI 90, PASI 100 and IGA 0 or 1 response over time

Summary statistics for PASI 75, PASI 90, PASI 100 and IGA 0 or 1 response by visit will be presented in contingency tables and will include absolute and relative frequencies.

Confidence intervals for response rates will be derived as well.

For PASI 75, PASI 90, PASI 100 and IGA 0 or 1 response at each visit, each secukinumab dose regimen will be compared to placebo (up to Week 12 only) [REDACTED] by exact logistic regression with treatment group, baseline bodyweight stratum, age stratum and baseline PASI score as explanatory variables.

For PASI 75, PASI 90 and IGA 0 or 1 response, the placebo-adjusted response rates including 95% confidence interval will be derived by visit up to Week 12. [REDACTED]

Additional summary analysis will be performed for PASI and IGA response by IRT dosing error and by body weight and dose group. See [Section 4.1](#) for details.

Figures will also be provided.

### **PASI score over time**

Summary statistics will be provided for absolute PASI scores as well as for percent change from baseline by visit and treatment group. Figures will also be provided.

[figure not shown]
The IRT dosing error affected subjects will be listed for PASI score.

Percent change from baseline of PASI score (observed cases) will be presented as Spaghetti plot in which the IRT dosing error affected subjects are not shown after Week 12.

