### **2.2 Secondary objectives**

- To demonstrate superiority of secukinumab (low and high dose) in subjects with severe chronic plaque psoriasis with respect to PASI 90 response at Week 12, compared to placebo.
- To assess efficacy of secukinumab in subjects with severe chronic plaques psoriasis with respect to PASI 50 and PASI 100 at Week 12, compared to placebo.
- To assess efficacy of secukinumab in subjects with severe chronic plaque psoriasis with respect to PASI 50, PASI 75, PASI 90 , PASI 100 and IGA mod 2011 0 or 1 at Week 16 and over time up to Week 52.
- To assess the efficacy of secukinumab with respect to changes in PASI score and IGA mod 2011 score at Week 12, compared to placebo, and over time up to Week 52.
- To investigate the effects of treatment with secukinumab with respect to changes in CDLQI at Week 12, compared to placebo, and over time up to Week 52.
- To investigate the effects of treatment of secukinumab with respect to CDLQI 0 or 1 achievement at Week 12, compared to placebo, and over time up to Week 52.
- To evaluate the effects of treatment of secukinumab on disability at Week 12 and over time up to Week 52 by use of the Childhood Health Assessment Questionnaire (CHAQ®), for subjects with history of psoriatic arthritis.
- To investigate the clinical safety and tolerability of secukinumab as assessed by growth, weight gain, tolerability of s.c. injections, vital signs, clinical laboratory variables, ECGs, and adverse events monitoring, compared to placebo.

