
## 1.2 Study objectives and endpoints

The primary objective of the study is to demonstrate the superiority of secukinumab (low and high dose) in pediatric subjects with severe chronic plaque psoriasis with respect to both PASI

75 and IGA mod 2011 0 or 1 response (co-primary endpoints) at Week 12, compared to placebo.

Following are the secondary objectives:

- To demonstrate superiority of secukinumab (low and high dose) in subjects with severe chronic plaque psoriasis with respect to PASI 90 response at Week 12, compared to placebo.
- To assess efficacy of secukinumab in subjects with severe chronic plaques psoriasis with respect to PASI 50 and PASI 100 at Week 12, compared to placebo.
- To assess efficacy of secukinumab in subjects with severe chronic plaque psoriasis with respect to PASI 50, PASI 75, PASI 90, PASI 100 and IGA mod 2011 0 or 1 at Week 16 and over time up to Week 52 (will consider up to week 24, for Week 24 PEA).
- To assess the efficacy of secukinumab with respect to changes in PASI score and IGA mod 2011 score at Week 12, compared to placebo, and over time up to Week 52 (will consider up to week 24, for Week 24 PEA).
- To investigate the effects of treatment with secukinumab with respect to changes in CDLQI at Week 12, compared to placebo, and over time up to Week 52 (will consider up to week 24, for Week 24 PEA).
- To investigate the effects of treatment of secukinumab with respect to CDLQI 0 or 1 achievement at Week 12, compared to placebo, and over time up to Week 52 (will consider up to week 24, for Week 24 PEA).
- To evaluate the effects of treatment of secukinumab on disability at Week 12 and over time up to Week 52 (will consider up to week 24, for Week 24 PEA) by use of CHAQ®, for subjects with history of psoriatic arthritis.
- To investigate the clinical safety and tolerability of secukinumab as assessed by growth, weight gain, tolerability of s.c. injections, vital signs, clinical laboratory variables, ECGs, and adverse events monitoring, compared to placebo.

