**Table 2-10 Overview of analysis methods for efficacy variables**

| Variable(s)  | Summary statistics for binary/ categorical data | Exact Logistic regression | Summary Statistics for continuous data | Time-to-event analysis | Graphs |
|--|---|---------------------------|--|------------------------|--------|
| PASI 75 at Week 12, compared to Placebo                      | X   | X                         |  |                        | X      |
| IGA mod 2011 0 or 1 response at Week 12, compared to Placebo | X   | X                         |  |                        | X      |
| PASI 90 response at Week 12, compared to Placebo             | X   | X                         |  |                        | X      |

| Variable(s)   | Summary statistics for binary/ categorical data | Exact Logistic regression | Summary Statistics for continuous data | Time-to-event analysis | Graphs |
|---|---|---------------------------|--|------------------------|--------|
| PASI 50/75/90/100 response over time                    | X   | X                         |  |                        | X      |
| IGA mod 2011 0 or 1 response over time                  | X   | X                         |  |                        | X      |
| PASI score over time, compared to Placebo               |   |                           | X                                      |                        | X      |
| IGA mod 2011 score over time, compared to Placebo       | X   |                           |  |                        |        |
| Change in CDLQI over time up to Week 52                 |   |                           | X                                      |                        |        |
| CDLQI 0 or 1 achievement over time, compared to Placebo | X   |                           |  |                        | X      |
| CHAQ score over time                                    |   |                           | X                                      |                        |        |
| CHAQ response over time                                 | X   |                           |  |                        |        |
|   |   |                           |  |                        |        |

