### 2.15.1 Children's Quality of Life Index (CDLQI)

The Children's Dermatology Life Quality Index ([Lewis-Jones and Finlay, 1995](#)) is a 10-item general dermatology disability index designed to assess health-related quality of life in pediatric subjects aged 4 to 16 years. It is self-explanatory and may be completed by the child with assistance from parents or caregivers as necessary.

The 10 questions cover six areas of daily activities including symptoms and feelings, leisure, school or holidays, personal relationships, sleep and treatment. The questions are based on the preceding week to permit accurate recall.

Each question is answered on a 4-point Likert scale scored from 0 to 3. These are added to give a minimum score of 0 and maximum score of 30. A higher CDLQI score indicated greater degree of QoL impairment. CDLQI is available in two versions, text only and text with cartoons. The text only version will be used in this study. The mean completion time of the text version is 120 seconds. The purpose of the CDLQI in this study is to investigate the effects of treatment of secukinumab with respect to CDLQI at Week 12, compared to placebo, and over time up to Week 52. This questionnaire should be completed in the language the subject is most familiar with before any other clinical assessments. The questionnaire should be completed by the subject with the help of parent/custodian if and as needed. The site staff may help understand the questions, as necessary. The subject should be given sufficient space and time to complete the questionnaire. The study coordinator should check the questionnaire for completeness and encourage the subject to complete any missing responses before the clinical examination. The CDLQI questionnaire will be completed by the subject.

For each of the seven scores, the percentage change from baseline will be derived. Summary statistics will be provided for absolute values as well as for the percentage change by visit and treatment group. The summary statistics will be presented for subjects till age  $<18$  years and a figure of change from baseline in CDLQI total score over time will be provided. An additional report will be created which will include only CDLQI assessments performed by subjects who were  $<16$  years of age at time of assessment.

CDLQI 0 or 1 achievement will be also analyzed by visit and over time until week 104 as previously specified in [Section 2.7.3](#).

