### 5.2.5 Other imputations

Only PASI and IGA mod 2011 based response variables are imputed with multiple imputation or non-response (see [Section 2.6.4](#)), other response variables (e.g. CDLQI 0 or 1 achievement) will be imputed with LOCF.

For CDLQI, CHAQ scores, missing values will be replaced by LOCF. Baseline values will not be carried forward. If no pre-treatment value exists, then values obtained after first dose of treatment can be used as baseline only if it was collected on the same day as first dose. In addition, missing baseline (PROs) values will be replaced by the means or modes of non-missing baseline values stratified by age group (<12 years or >=12 years) and sex, for continuous scale or categorical/ordinal scale, respectively.

The laboratory test values below the Lower Level of Quantification (LLQ) or above the Upper Level of Quantification (ULQ) will be imputed as LLQ or ULQ value, respectively. The numerical part of the reported result will be treated as the actual LLQ or ULQ. These laboratory values will be displayed in listings using the standard unit with the reported sign (“<” or “>”).

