## 5.6 Subject reported outcomes

### 5.6.1 CDLQI scoring

The scoring of each question is as follows:

- Very much: Scored 3
- A lot: Scored 2
- A little: Scored 1
- Not at all: Scored 0
- Not relevant: Scored 0
- Question unanswered: Scored 0
- Question 7: "prevented school ": Scored 3

The CDLQI total score will be calculated by summing the score of each question resulting in a maximum of 30 and a minimum of 0. The higher the score, the more Quality of Life is impaired.

Meaning of CDLQI Scores

- 0-1= no effect at all on subject's life
- 2-6= small effect on subject's life
- 7-12= moderate effect on subject's life
- 13-18= very large effect on subject's life
- 19-30= extremely large effect on subject's life

The CDLQI will be analyzed under six headings as follows:

- Symptoms and feelings: questions 1 and 2, score maximum 6
- Leisure: questions 4, 5 and 6, score maximum 9
- Holidays or school: question 7, score maximum 3
- Personal relationships: questions 3 and 8: score maximum 6
- Sleep: question 9, score maximum 3
- Treatment: question 10, score maximum 3

Interpretation of incorrectly completed questionnaires:

There is a very high success rate of accurate completion of the CDLQI. However, sometimes subjects do make mistakes.

1. If one question is left unanswered, then this is scored 0.

2. If two or more questions are left unanswered, then the questionnaire will not be scored.
3. If two or more response options are ticked, the response option with the highest score will be recorded.
4. If there is a response between two tick boxes, the lower of the two score options will be recorded.
5. If one item is missing from a two- item subscale, then that subscale will not be scored.

Handling of missing values:

- If there is only one missing score per visit, it will be imputed with 0, and then the subscale including this item and the total score will be derived accordingly.
- If there are two or more missing scores per visit, then LOCF will be applied to the subscale scores, and total score, separately (i.e. LOCF is NOT applied to the 10 individual question scores for further derivation of the 6 subscale scores and 1 total score).

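### The Week 12 objectives on change in PASI score and change in CDLQI are worded as comparisons with placebo, but no between-arm difference is pre-specified for either, and CDLQI percentage change has no rule for a baseline of 0

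*SAP*

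**What the plan says.** **Objectives.** SAP 1.2 states: "To assess the efficacy of secukinumab with respect to changes in PASI score and IGA mod 2011 score at Week 12, compared to placebo". It words the CDLQI objective the same way: "with respect to changes in CDLQI at Week 12, compared to placebo". Protocol 2.2 matches. CDLQI 0 or 1 achievement is a separate objective.

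**PASI score.** SAP 2.7.3: "Summary statistics will be provided for absolute PASI scores as well as for percent change from baseline by visit and treatment group". Figures are added. The Table 2-10 row reads "PASI score over time, compared to Placebo", but only continuous summary statistics and graphs are ticked. SAP 2.8.2 (hypothesis, model, method for secondary objectives) and SAP 2.8.3 (missing values) are both entered as not applicable.

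**CDLQI.** SAP 2.15.1: "For each of the seven scores, the percentage change from baseline will be derived". Absolute values and percentage change are then summarised by visit and arm. SAP 4 removes the stratified Van Elteren test and the Hodges-Lehmann estimate for the total score.

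**Missing data.** SAP 5.2.5: "Only PASI and IGA mod 2011 based response variables are imputed with multiple imputation or non-response". CDLQI scores use LOCF, and missing PRO baselines are filled from means or modes by age group and sex. SAP 5.1.2.3 imputes PASI score and its change in 100 data sets on the way to the response variables.

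**Scale.** SAP 5.6.1 makes three CDLQI subscales single items, for example "Holidays or school: question 7, score maximum 3". Sleep and treatment are the other two.

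**The concern.** Two stated objectives ask how change on secukinumab compares with change on placebo, and the plan defines no quantity that answers them. Anyone who later computes a difference must choose the scale (absolute or percent), the covariates and the handling of missing PASI scores with the data already known.

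For CDLQI subscales, percentage change divides by the baseline. A child at 0 has no value and leaves that summary. Such a child can only stay level or worsen, so the exclusion is not neutral.

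**Working it through.** **1. The plan's own figures.** SAP 3 gives power with 40 per arm, one-sided 1.25%, Fisher's exact test. Full enumeration of the two binomials gives:

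| Endpoint | Rates | Stated | Recomputed |
|---|---|---|---|
| PASI 75 | 10% vs 65% | about 99% | 99.9% |
| IGA 0/1 | 10% vs 45% | about 88% | 88.4% |
| PASI 90 | 8% vs 39% | about 82% | 82.1% |

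These reproduce, but they concern responses. Neither document gives an SD or an effect size for change in PASI or CDLQI, so what follows is in SD units or rests on labelled assumptions.

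**2. Objective against method.**

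| Objective (Week 12, against placebo) | Between-arm method in the SAP |
|---|---|
| PASI 50/75/90/100 response | Exact logistic regression (2.7.3, Table 2-10, 5.1.2.2) |
| CDLQI 0 or 1 | Fisher's exact test (2.7.3) |
| Change in PASI score | None; by-arm summaries and figures |
| Change in CDLQI | None; the total-score method was removed |

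SAP 2.8.1 refers secondary endpoints to the primary instructions, but exact logistic regression does not apply to a continuous score.

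**3. What a difference would show.** 95% half-width = 1.96 × √(2/n) SD. With n = 40: 1.96 × √0.05 = 0.44 SD.

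**4. Zero baseline.** Percentage change = 100 × (post − baseline)/baseline, undefined at baseline 0. The share of children at 0 is not given, so a range is assumed, equal in both arms:

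| Assumed share at 0 | Children of 40 with a percentage change | Half-width (SD) |
|---|---|---|
| 0% | 40 | 0.44 |
| 10% | 36 | 0.46 |
| 20% | 32 | 0.49 |
| 40% | 24 | 0.57 |
| 50% | 20 | 0.62 |

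Even at an assumed 5%, the chance that an arm of 40 contains at least one such child is 1 − 0.95^40 = 87%. PASI is not exposed: Protocol 6.4.2 requires a baseline of at least 20.

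**5. Open missing-data rule for PASI (illustration, all values assumed).** Suppose children with a Week 12 score improve by 85% on average, and those without one would have improved by 0%. The observed-case mean stays at 85%. The mean over all 40 is 38 × 85/40 = 80.75% with 2 missing, and 36 × 85/40 = 76.5% with 4 missing. The documents give no missingness figure. Children who stop treatment are still scheduled for an end-of-induction visit, so missingness may be small.

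**The case against.** **Descriptive treatment looks deliberate.** The objectives reserve demonstrating superiority for PASI 75, IGA 0/1 and PASI 90; change scores are only to be assessed or investigated. Protocol 9.5.2 and 9.5.5 plan the same by-arm summaries. Amendment 4 explains that the CDLQI total-score test went because CDLQI 0 or 1 was already compared with controls. This stands as a reason for having no formal test. It does not supply an estimate for a comparative objective, and CDLQI change and CDLQI 0 or 1 are separate objectives.

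**A reader might infer that no between-arm effect can be reported.** The documents do not support that. By-arm n, mean and SD yield an unadjusted difference. With assumed mean changes of −7 and −2, SD 6 and 40 per arm, it is −5.0, with SE √(36/40 + 36/40) = 1.34 and 95% CI −7.6 to −2.4. PASI response and CDLQI 0 or 1 are also compared with placebo.

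**A reader might infer that the CDLQI summaries ignore missing data, or that the PASI table is observed-case.** CDLQI has LOCF and baseline imputation; only a child with no post-baseline value stays missing. For PASI, only the spaghetti plot is labelled observed cases. The table's method is unstated, which is a gap and not a stated choice.

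**A reader might infer that percent is the only scale, or that it is unbounded for worsening.** SAP 5.1.1 gives absolute change for PASI and the CDLQI total, and absolute values are summarised for every CDLQI score. Subscale absolute change rests only on the general rule in SAP 2.1. Percent change is bounded: at most +200% on a 0 to 3 item (1 to 3), and +260% for PASI from 20 (20 to 72).

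**Conclusion.** The point holds in a limited form. No between-arm difference, interval or adjustment is pre-specified for change in PASI score or change in CDLQI at Week 12, although both objectives are set against placebo. Missing-data handling for the continuous PASI summary is unstated. CDLQI percentage change has no rule for a zero baseline, so affected children leave the subscale percentage-change summary, in numbers the documents do not reveal.

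The effect on the trial's main conclusions is nil: H1 to H6, the response comparisons, PASI percentage change and the CDLQI total's absolute change are unaffected. What is lost is a defined estimate for two secondary objectives, obtainable with a half-width of about 0.44 SD if 40 children per arm contribute. The zero-baseline shares and the missing-PASI example are assumptions, not findings about this trial.

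**What to change.** - **PASI.** For Week 12 change, fit an ANCOVA with treatment, age stratum, weight stratum and baseline PASI in each of the existing 100 imputed data sets. Pool by Rubin's rules and report each dose minus placebo with a 95% CI. State the missing-data method for the PASI score summaries. The printed imputation code stops at the primary-endpoint week, so say separately what applies to later visits.
- **CDLQI.** Summarise absolute change for all seven scores. For the total at Week 12, fit an ANCOVA with treatment, baseline CDLQI and the two strata. Use the SAP's own CDLQI missing-data rule, because the imputed data sets contain no CDLQI.
- **Status.** Report these as descriptive, outside H1 to H6, and list them in SAP 4.1 with the other analyses added after the Week 24 database lock.

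The cost is a little programming and post-hoc status, which must be stated. If the sponsor prefers no between-arm estimate, the minimum is to reword the two objectives and the Table 2-10 row as descriptive and to add a zero-baseline rule.
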